### 6.8.1. Rescue Medicine

Standard medical supportive care may be provided to manage AEs.

# 7. DISCONTINUATION OF STUDY INTERVENTION AND PARTICIPANT DISCONTINUATION/WITHDRAWAL

### 7.1. Discontinuation of Study Intervention

It may be necessary for a participant to permanently discontinue study intervention. Reasons for permanent discontinuation of study intervention include the following.

- AE of Grade 3 severity or greater and considered by the investigator to be related to study intervention;
- SAE considered by the investigator to be related to study intervention;
- Requirement for prohibited concomitant medication;
- Death;
- Pregnancy;
- Study terminated by sponsor;
- Withdrawal by participant or legally authorized representative
- Miss more than 2 consecutive doses of study intervention.

In the event a participant is hospitalized, study intervention may continue to be administered, as feasible, and based on medical judgement of the investigator.

Note that discontinuation of study intervention does not represent withdrawal from the study. If study intervention is permanently discontinued, the participant will remain in the study to be evaluated for all subsequent scheduled assessments. See the SoA for data to be collected at the time of discontinuation of study intervention and follow-up for any further evaluations that need to be completed.

In the event of discontinuation of study intervention, it must be documented on the appropriate CRF/in the medical records whether the participant is discontinuing further receipt of study intervention or also from study procedures, posttreatment study follow-up, and/or future collection of additional information.

### 7.1.1. Potential Cases of Decreased eGFR

If postscreening eGFR is  $<45 \text{ mL/min}/1.73\text{m}^2$  the participant will be instructed to discontinue any remaining study intervention doses as soon as study staff become aware of the eGFR results.

### 7.2. Participant Discontinuation/Withdrawal From the Study

A participant may withdraw from the study at any time at his/her own request. Reasons for discontinuation from the study include the following:

- Refused further study procedures;
- Lost to follow-up;
- Death;
- Study terminated by sponsor.

At the time of discontinuing from the study, if possible, an early discontinuation visit should be conducted. See the SoA for assessments to be collected at the time of study discontinuation and follow-up and for any further evaluations that need to be completed.

The early discontinuation visit applies only to participants who are enrolled/randomized and then are prematurely withdrawn from the study. Participants should be questioned regarding their reason for withdrawal.

If a participant withdraws from the study, he/she may request destruction of any remaining samples taken and not tested, and the investigator must document any such requests in the site study records and notify the sponsor accordingly.

If the participant withdraws from the study and also withdraws consent (see Section 7.2.1) for disclosure of future information, no further evaluations should be performed and no additional data should be collected. The sponsor may retain and continue to use any data collected before such withdrawal of consent.

## 7.2.1. Withdrawal of Consent

Participants who request to discontinue receipt of study intervention will remain in the study and must continue to be followed for protocol specified follow up procedures. The only exception to this is when a participant specifically withdraws consent for any further contact with him or her or persons previously authorized by the participant to provide this information. Participants should notify the investigator in writing of the decision to withdraw consent from future follow up, whenever possible. The withdrawal of consent should be explained in detail in the medical records by the investigator, as to whether the withdrawal is only from further receipt of study intervention or also from study procedures and/or posttreatment study follow up, and entered on the appropriate CRF page. In the event that vital status (whether the participant is alive or dead) is being measured, publicly available information should be used to determine vital status only as appropriately directed in accordance with local law.

### 7.3. Lost to Follow Up

A participant will be considered lost to follow up if he or she repeatedly fails to return for scheduled visits and is unable to be contacted by the study site.

The following actions must be taken if a participant fails to be available for a required study visit:

- The site must attempt to contact the participant and reschedule the missed visit as soon as possible. Counsel the participant on the importance of maintaining the assigned visit schedule, and ascertain whether the participant wishes to and/or should continue in the study;
- Before a participant is deemed lost to follow up, the investigator or designee must make every effort to regain contact with the participant (where possible, 3 telephone calls and, if necessary, a certified letter to the participant's last known mailing address or local equivalent methods). These contact attempts should be documented in the participant's medical record;
- Should the participant continue to be unreachable, he/she will be considered to have withdrawn from the study.

### 8. STUDY ASSESSMENTS AND PROCEDURES

The investigator (or an appropriate delegate at the investigator site) must obtain a signed and dated ICD before performing any study specific procedures.

Study procedures and their timing are summarized in the SoA. Protocol waivers or exemptions are not allowed.

Safety issues should be discussed with the sponsor immediately upon occurrence or awareness to determine whether the participant should continue or discontinue study intervention.

Adherence to the study design requirements, including those specified in the SoA, is essential and required for study conduct.

All screening evaluations must be completed and reviewed to confirm that potential participants meet all eligibility criteria. The investigator will maintain a screening log to record details of all participants screened and to confirm eligibility or record reasons for screening failure, as applicable.

Procedures conducted as part of the participant's routine clinical management (eg, blood count) and obtained before signing of the ICD may be utilized for screening or baseline purposes provided the procedures met the protocol-specified criteria and were performed within the time frame defined in the SoA.

PFIZER CONFIDENTIAL

Page 47

In the event a participant is hospitalized, study assessments should be performed as feasible. Procedures not performed due to hospitalizations would not be considered protocol deviations.

Every effort should be made to ensure that protocol-required tests and procedures are completed as described. However, it is anticipated that from time to time there may be circumstances outside the control of the investigator that may make it unfeasible to perform the test. In these cases, the investigator must take all steps necessary to ensure the safety and well-being of the participant. When a protocol-required test cannot be performed, the investigator will document the reason for the missed test and any corrective and preventive actions that he or she has taken to ensure that required processes are adhered to as soon as possible. The study team must be informed of these incidents in a timely manner.

For samples being collected and shipped, detailed collection, processing, storage, and shipment instructions and contact information will be provided to the investigator site prior to initiation of the study.

The total blood sampling volume for individual participants in this study is approximately 150 mL. There will be an additional optional up to 4 mL of blood collected for a subset of participants who agree to collect an optional PK sample. The actual collection times of blood sampling may change. Additional blood samples may be taken for safety assessments at times specified by Pfizer, provided the total volume taken during the study does not exceed 550 mL during any period of 56 consecutive days.

## 8.1. Efficacy Assessments

## 8.1.1. Participant Diary

Participants will be provided an electronic handheld device or will use their own device to record daily COVID-19 signs and symptoms, study intervention administration, and PRO assessments in the study diary.

Participants will receive daily reminders to complete entries on their own as specified in the SoA. The diary should be completed at approximately the same time every day. Staff will review the participant's study diary online as specified in the SoA.

The diary allows recording of these assessments only within a fixed time window (eg, 24h), thus providing an accurate representation of the participant's experience at that time. The participant is able to make revisions to incorrect entries before pressing the save or submit button. In the event that a participant becomes aware of an error in data after the entry is saved, a change to the diary data may only be made by the investigator submitting a data clarification form. Data reported in the participant diary will be transferred electronically to a third-party vendor, where they will be available for review by investigators and the sponsor or delegate at all times via an internet-based portal.

## 8.1.2. COVID-19-Related Medical Visit Details

Details of participants' COVID-19-related medical visits (ie, hospitalization, practitioner's office, home healthcare services, telemedicine, urgent care, emergency room ≤24h, extended

care facility stay) will be collected during study visits, including level of care (ICU status) and dates of utilization, including admission and discharge, as applicable.

Hospitalization is defined as >24 hours of acute care, in a hospital or similar acute care facility, including Emergency Rooms or temporary facilities instituted to address medical needs of those with severe COVID-19 during the COVID-19 pandemic. This includes specialized acute medical care unit within an assisted living facility or nursing home. This does not include hospitalization for the purposes of public health and/or clinical trial execution.

## 8.1.3. Daily Signs and Symptoms of COVID-19

On Day 1, participants will complete the study diary before receiving study intervention. Participant assessment of COVID-19-related symptoms should be recorded at approximately the same time each day as specified in the SoA and described in Section 8.1.1.

COVID-19-related symptoms will be evaluated in accordance with FDA guidelines (Appendix 10). Participants will record a daily severity rating of their symptom severity over the past 24 hours based on a 4-point scale in which 0 is reported if no symptoms were present; 1 if mild; 2 if moderate; and 3 if severe.

Vomiting and diarrhea will each be rated on a 4-point frequency scale where 0 is reported for no occurrence, 1 for 1 to 2 times, 2 for 3 to 4 times, and 3 for 5 or greater.

Sense of smell and sense of taste will each be rated on a 3-point Likert scale where 0 is reported if the sense of smell/taste was the same as usual, 1 if the sense of smell/taste was less than usual, and 2 for no sense of smell/taste.

Targeted COVID-19-associated symptoms are a subset of these symptoms (Appendix 9).

## 8.1.4. Oxygen Support Details

Type of oxygen support (eg, oxygen supplementation received at home, mechanical ventilation received in hospital) will be collected.

## 8.1.5. PRO Assessments

## 8.1.5.1. Global Impression Questions

Three questions will be included in the ePRO to assess patient-reported global impression items: a) return to usual health; b) return to usual activities; and c) overall COVID-19-related symptoms.

## 8.1.5.2. WPAI

COVID-19 impacts manual and office-based work, and results in missed work due to illness or quarantine and loss in of productivity. The Work Productivity and Activity Impairment Questionnaire: General Health (GH) is being implemented for COVID-19 (ie., WPAI-COVID-19) in order to evaluate change from baseline in work burdens. The WPAI-GH has demonstrated validity, reliability and sufficient predictive value to measure the impact of

disease on absenteeism, presenteeism, and overall productivity in a manner that can also be monetized.

The WPAI-COVID-19 consists of 6 questions that refer to the following assessments for work productivity: 1 = currently employed, 2 = hours missed due to health problems, 3 = hours missed other reasons, 4 = hours actually worked, 5 = degree health affected productivity while working (using a 0 to 10 VAS), and 6 = degree health affected productivity in regular unpaid activities. The recall period for questions 2 through 6 is 7 days. Four main outcomes will be generated from the WPAI-COVID-19 and reported as: 1) percent work time missed due to COVID-19 for those who are currently employed, 2) percent impairment while working due to COVID-19 for those who are currently employed and actually worked in the past 7 days, 3) percent overall work impairment due to COVID-19 for those who are currently employed, and 4) percent activity impairment due to COVID-19 for all respondents. The WPAI-COVID-19 will be completed during site visits, as specified in the SoA.

## 8.1.5.3. EQ-5D-5L Scale

The EQ-5D is a validated, standardized, generic instrument that is a preference-based health related quality of life questionnaire in cost effectiveness and health technologies assessment (HTA). Recently, a version was developed called EQ-5D-5L with 5 response levels on each dimension compared to the 3 response levels in the Euroquol Quality of Life 5-Dimension 3-Level Scale (EQ-5D-3L).

Measurement properties of the EQ-5D-5L demonstrated to be a valid version of the 3 level questionnaire that improved measurements by adding discriminatory power, reducing the ceiling, and establishing convergent and known groups validity. Both the EuroQol EQ-5D-3L and EQ-5D-5L versions are well established instruments used to measure health states and utilities in various diseases areas and assess mobility, self care, usual activities, pain/discomfort, anxiety/depression and health status using a VAS. The EQ-5D-5L should be completed as described in the Schedule of Activities.

### 8.2. Safety Assessments

Planned time points for all safety assessments are provided in the SoA. Unscheduled clinical laboratory measurements may be obtained at any time during the study to assess any perceived safety issues.

## 8.2.1. Medical History

Medical history in addition to COVID-19 disease history and demographics will be collected at screening. Smoking status will be collected. Complete medication history of all prescription or nonprescription drugs (including vaccinations), and dietary and herbal supplements taken within 30 days prior to the planned first dose will be collected.

## 8.2.2. Height and Weight

Height and weight will also be measured and recorded at screening. Height may be self reported.

### 8.2.3. Targeted Physical Examinations

A targeted physical examination will include, at a minimum, cardiopulmonary assessments. Investigators should pay special attention to any previously identified or new AE/targeted condition that the participant has experienced.

Physical examination findings collected during the study will be considered source data and will not be required to be reported, unless otherwise noted. Any untoward physical examination findings that are identified during the active collection period and meet the definition of an AE or SAE (Appendix 3) must be reported according to the processes in Sections 8.3.1 to 8.3.3.

## 8.2.4. Vital Signs

Temperature, pulse rate, respiratory rate, oxygen saturation level, and blood pressure will be assessed as specified in the SoA.

Blood pressure and pulse rate measurements will be assessed with the participant in the supine or seated position with their feet on the floor when possible with a completely automated device. It is recommended that the same position should be used for a participant throughout the study duration. Manual techniques will be used only if an automated device is not available.

Blood pressure and pulse rate measurements should be preceded by at least 5 minutes of rest for the participant in a quiet setting without distractions (eg, television, cell phones).

Vital signs are to be taken before blood collection for laboratory tests.

Each participant will also be supplied with a pulse oximeter to be used based on the instruction and medical judgment of the site investigator.

### 8.2.5. Electrocardiograms

Standard 12-lead ECGs utilizing limb leads (with a 10 second rhythm strip) should be collected at times specified in the SoA section of this protocol using an ECG machine that automatically calculates the heart rate and measures PR, QT, and QTc intervals and QRS complex. Alternative lead placement methodology using torso leads (eg, Mason-Likar) should not be used given the potential risk of discrepancies with ECGs acquired using standard limb lead placement. All scheduled ECGs should be performed after the participant has rested quietly for at least 10 minutes in a supine position. Triplicate 12-lead ECGs obtained at a minimum at baseline/Day 1, should be obtained approximately 2 to 4 minutes apart.

ECG data may be submitted to a central laboratory for measurement. The final ECG report from the central laboratory should be maintained in the participant's source documentation and be the final interpretation of the ECG recording. Any clinically significant changes from the baseline/Day 1 ECG may potentially be AEs (Appendix 7) and should be evaluated further, as clinically warranted

If a) a postdose QTcF interval remains  $\geq 60$  msec from the baseline and is >450 msec; or b) an absolute QT value is  $\geq 500$  msec for any scheduled ECG for greater than 4 hours (or sooner, at the discretion of the investigator); or c) QTcF intervals get progressively longer, the participant should undergo continuous ECG monitoring.

In some cases, it may be appropriate to repeat abnormal ECGs to rule out improper lead placement as contributing to the ECG abnormality. It is important that leads be placed in the same positions each time in order to achieve precise ECG recordings. If a machine read QTc value is prolonged, as defined above, repeat measurements may not be necessary if a qualified medical provider's interpretation determines that the QTcF values are in the acceptable range.

ECG values of potential clinical concern are listed in Appendix 7.

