## 10.7. Appendix 7: ECG Findings of Potential Clinical Concern

#### ECG Findings That May Qualify as AEs

- Marked sinus bradycardia (rate <40 bpm) lasting minutes.
- New PR interval prolongation >280 msec.
- New prolongation of QTcF to >480 msec (absolute) or by  $\geq$ 60 msec from baseline.
- New-onset atrial flutter or fibrillation, with controlled ventricular response rate: ie, rate <120 bpm.
- New-onset type I second-degree (Wenckebach) AV block of >30 seconds' duration.
- Frequent PVCs, triplets, or short intervals (<30 seconds) of consecutive ventricular complexes.

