## ECG Findings That May Qualify as SAEs

- QTcF prolongation >500 msec.
- New ST-T changes suggestive of myocardial ischemia.
- New-onset left bundle branch block (QRS >120 msec).
- New-onset right bundle branch block (QRS >120 msec).
- Symptomatic bradycardia.
- Asystole:
  - In awake, symptom-free patients in sinus rhythm, with documented periods of asystole  $\geq$ 3.0 seconds or any escape rate <40 bpm, or with an escape rhythm that is below the AV node;
  - In awake, symptom-free patients with atrial fibrillation and bradycardia with 1 or more pauses of at least 5 seconds or longer;
  - Atrial flutter or fibrillation, with rapid ventricular response rate: rapid = rate >120 bpm.
- Sustained supraventricular tachycardia (rate >120 bpm) ("sustained" = short duration with relevant symptoms or lasting >1 minute).

- Ventricular rhythms >30 seconds' duration, including idioventricular rhythm (heart rate <40 bpm), accelerated idioventricular rhythm (HR 40 bpm to <100 bpm), and monomorphic/polymorphic ventricular tachycardia (HR >100 bpm (such as torsades de pointes)).
- Type II second-degree (Mobitz II) AV block.
- Complete (third-degree) heart block.

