6.6.4. Electrocardiograms

Central reader will provide the reading of all ECG parameters. Descriptive statistics will be provided for change from baseline to each measurement time for heart rate, PR interval, QRS width, QT interval and QTcF (Fridericia correction) values. Baseline will be defined as the mean of the pre-dose triplicates at the Baseline Visit. Additionally, the incidence of categorical increases in QTc intervals will be provided. Categories for QTcF are \geq 450 msec, \geq 480 msec, and \geq 500 msec. Categories for QTcF as change from baseline are \geq 30 msec increase and \geq 60 msec increase. QTcF is considered the primary QTc value for measurements of change and for clinical decision making as this correction is more accurate with changes in heart rate.

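### Minor: the absolute 500 msec trigger for continuous ECG monitoring (Protocol 8.2.5) names uncorrected QT, so above 60 bpm a QTcF of 500 msec or more can meet no trigger

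*Protocol*

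**What the plan says.** Protocol 8.2.5 calls for continuous ECG monitoring in any of three situations:

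- (a) postdose QTcF remains at least 60 msec from baseline and is also above 450 msec;
- (b) "an absolute QT value is" at or above 500 msec, "for any scheduled ECG for greater than 4 hours (or sooner, at the discretion of the investigator");
- (c) QTcF lengthens progressively. No size of change or number of ECGs is given.

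The next paragraph of the same section says: "If a machine read QTc value is prolonged, as defined above, repeat measurements may not be necessary", provided a qualified provider finds the QTcF values acceptable.

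Other sections set absolute limits on QTcF. Protocol Appendix 7 lists an absolute QTcF above 480 msec as a possible AE and "QTcF prolongation >500 msec" as a possible SAE. SAP 6.6.4 tabulates QTcF at or above 500 msec and states: "QTcF is considered the primary QTc value for measurements of change and for clinical decision making".

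The Schedule of Activities plans ECGs at Baseline and Days 3, 5 and 14 for the first 60 participants. Later ECGs depend on an E-DMC or FDA recommendation.

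**The concern.** Trigger (b) is the only absolute limit that stands alone, and the only one of the three not on QTcF. The documents do not say whether raw QT was deliberate. If it was, the monitoring rule has no absolute QTcF limit. If QT was shorthand for QTc, the wording does not say so and needs the same correction.

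What is at stake is participant safety, not inference. Raw QT shortens as heart rate rises, so a value that Appendix 7 treats as a possible SAE can sit below the raw-QT limit. QTc prolongation is a recognised issue in this protocol: Appendix 8 notes that both haloperidol and ritonavir lengthen QTc, and still allows haloperidol with caution. Section 5.2 sets no QTc exclusion limit, so participants may enter with a QTcF already above 440 msec.

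**Working it through.** The plan states no figure to reproduce. The check is whether an ECG with QTcF of 500 msec or more can miss every trigger.

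**Inputs.** The trigger limits come from Protocol 8.2.5. QTcF is the Fridericia correction (Protocol Appendix 12, SAP 6.6.4):

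QTcF = QT / (60/HR)^(1/3), so QT = QTcF × (60/HR)^(1/3).

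**Step 1: what (b) misses by itself.** The two measures agree only at 60 bpm. The last column is the QTcF in the third column minus 60. It is the baseline needed to miss (a) as well at the top of the range that (b) misses.

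| HR (bpm) | Raw QT when QTcF = 500 | QTcF when raw QT = 500 | Baseline QTcF needed at the top of the range |
|---|---|---|---|
| 50 | 531.3 | 470.5 | no gap |
| 55 | 514.7 | 485.7 | no gap |
| 60 | 500.0 | 500.0 | no gap |
| 65 | 486.8 | 513.5 | about 454 |
| 70 | 475.0 | 526.4 | about 466 |
| 80 | 454.3 | 550.3 | about 490 |
| 90 | 436.8 | 572.4 | about 512 |
| 100 | 421.7 | 592.8 | about 533 |

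At 70 bpm, for example, (b) misses QTcF values from 500 to just below 526 msec.

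**Step 2: add trigger (a).** (a) is missed only if the rise is under 60 msec. For an on-study QTcF of 500, the baseline must exceed 500 − 60 = 440 msec. With a baseline of 440 or below, any QTcF of 500 or more is a rise of at least 60 to above 450, so the (a) threshold is always reached.

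**Step 3: worked cases.**

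- Baseline 448, on-study QTcF 505 at 70 bpm. Rise = 505 − 448 = 57, so (a) is not met. Raw QT = 505 × (60/70)^(1/3) = 479.7, so (b) is not met.
- Baseline 445, raw QT 465 at 75 bpm. QTcF = 465 / (60/75)^(1/3) = 500.9, a rise of 55.9. Neither (a) nor (b) is met.
- Boundary: the second ECG with a baseline of 440 is a rise of 60.9, and (a) is reached. In the first case, an on-study QTcF of 508 (rise 60) would also reach (a).

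**Step 4: add trigger (c).** If QTcF in the first two cases then stays level or falls, there is no progressive lengthening and (c) is not met. No trigger applies.

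**Step 5: compare two rewordings of (b).**

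- Replacing QT with QTcF outright would lose triggers at slow rates: raw QT from 500 to 531 at 50 bpm, and from 500 to just below 515 at 55 bpm.
- Accepting either QTcF or raw QT at 500 loses nothing. A new trigger needs QTcF at or above 500 with QT below 500. That requires (60/HR)^(1/3) < 1, which is a rate above 60 bpm.

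**The case against.** The strongest reply is that QT in (b) is shorthand for QTc. The section never says uncorrected, its next paragraph treats the list as defining a prolonged QTc, and the SAP makes QTcF the decision measure. This is plausible. It makes the problem a drafting slip, but a site applying the text as written would still use raw QT.

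Several narrowing points stand:

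- (c) has no threshold, so an investigator could read a 57 msec rise across several ECGs as meeting it. Nothing obliges that reading, and a plateau after one step up does not fit it well.
- The rewording would keep the 4-hour or discretion clause, so a single QTcF of 505 would reach the threshold without automatically triggering monitoring. Likewise, (a) requires the rise to persist.
- The upper ends of the ranges in Step 1 need very high baselines. The realistic gap is values slightly above 500 with baselines slightly above 440.

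Other safeguards would bring such a value to attention. Section 8.2.5 says clinically significant changes "should be evaluated further, as clinically warranted". Appendix 7 recommends core-laboratory alerts for its listed findings, Section 8 sends safety issues to the sponsor immediately, and the Schedule of Activities allows unplanned visits. Section 7.1 stops dosing for an "SAE considered by the investigator to be related to study intervention". None of these requires continuous monitoring, which is what 8.2.5 exists to specify.

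Reach is also small. With 1:1 randomization, about 30 of the 60 sentinel participants receive active drug.

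**Conclusion.** The point holds and is minor. As written, a QTcF of 500 msec or more can meet no continuous-monitoring trigger when all of these coincide: heart rate above 60 bpm with raw QT below 500, a rise from baseline under 60 msec, and no progressive lengthening. At 60 bpm or below there is no gap.

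The conclusion rests on reading QT literally and on the Fridericia formula. How many participants would fall in the gap cannot be estimated from the documents.

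The sentinel ECGs were probably complete by Amendment 4. This is an inference from that amendment's statement that the 45% interim analysis had met its objective. The practical effect would then fall on any ECGs added later on E-DMC or FDA advice. No endpoint, estimand or efficacy analysis is touched, and the SAP's QTcF tabulation already covers values of 500 msec or more.

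**What to change.** In Protocol 8.2.5, reword (b) so that it applies when an absolute QTcF (or uncorrected QT) value is ≥500 msec, and leave the 4-hour and discretion clause as it is. Do not simply swap QT for QTcF, because that drops the slow-rate triggers shown in Step 5.

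The cost is one phrase in the next amendment or a clarification letter, issued before any further ECGs are requested. The ECG machines already report heart rate, QT and QTc. The only downside is a few additional monitoring triggers, all above 60 bpm. Appendix 7 and the SAP need no change.
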